	
 • By age categories defined as 40 to 54 years, 55 to 64 years, 65 to 74 years, and ≥ 75 years • By renal function categories (based on eGFR) defined as: < 30 ml/min/1.73m², 30 to 44 ml/min/1.73m², 45 to 59 ml/min/1.73m², 60 to 89 ml/min/1.73 m², ≥ 90 ml/min/1.73m², and not available • By race defined as White, African American, Asian, or Other/Unknown 
Secondary analysis
 
Comparisons of pre-index characteristics and outcome measures will be provided, and appropriate tests will be used based on the distribution of the measure. Continuous measures will be compared using t-tests and categorical measures will be compared using chi-square tests. P-values and 95% confidence intervals will be reported. Reported p-values will not be adjusted for multiple comparisons.
 
In addition to the descriptive analyses described above, multivariable modelling will be considered to assess change in HbA1c, controlling for an a priori list of covariates. The use of multivariable modelling will be dependent on having robust sample size distribution across age and eGFR categories.

Milestones:
	
Protocol Completion Data Extraction, Preparation & QA Data Analysis Final Report

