8. RESEARCH QUESTION AND OBJECTIVES

The purpose of this study is to assess glycemic control among adults with T2DM during the 60 to 180 days following initiation of linagliptin.

The primary study objective is to:

- Describe change in HbA1c among adults with T2DM within the 60 to 180 days following initiation of linagliptin across pre-defined age and renal function categories. Age categories will be defined as: 40 to 54 years, 55 to 64 years, 65 to 74 years, and ≥ 75 years. Renal function categories will be defined based on eGFR as: <30 ml/min/1.73m², 30 to 44 ml/min/1.73m², 45 to 59 ml/min/1.73m², 60 to 89 ml/min/1.73m², and ≥ 90 ml/min/1.73m².

The secondary study objectives are to:

- Compare change in HbA1c among adults with T2DM within 60 to 180 days following initiation of linagliptin across pre-defined age and renal function categories.
- Compare the proportion of adults with T2DM who achieve HbA1c $< 7.0\%$ within 60 to 180 days following initiation of linagliptin across the pre-defined age and renal function categories.

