9.2.2 Inclusion Criteria

To be included in the study sample, patients must meet all of the following criteria:

- ≥ 1 written prescription for linagliptin (Tradjenta[®], Jentaducto[®], or Jentaducto XR[®]) in the EHR data during the identification period (medication codes for index medications in Table 1 of [Annex 1, Appendix B](#))
- ≥ 40 years of age based on the year of the index date
- First active date in the EHR is ≥ 180 days prior to the index date
- ≥ 1 diagnosis code representing T2DM in the EHR data during the 180-day pre-index period or on the index date (diagnosis codes in Annex 1, Appendix A)
- ≥ 1 HbA1c value during the 180-day pre-index period or on the index date
- ≥ 1 HbA1c value 60 to 180 days after the index date

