9.3.2.2 Secondary outcomes

The secondary outcome variable, HbA1c goal attainment, as defined below, will be evaluated among the overall study sample and stratified across pre-defined age and renal function categories. Age categories will be defined as: 40 to 54, 55 to 64, 65 to 74, and ≥ 75 years. Renal function categories will be defined based on eGFR as: < 30 ml/min/1.73m², 30 to 44 ml/min/1.73m², 45 to 59 ml/min/1.73m², 60-89 ml/min/1.73m², and ≥ 90 ml/min/1.73m².

- HbA1c goal attainment—A binary variable will be created to designate HbA1c goal attainment 60 to 180 days after the index date. HbA1c goal attainment will be defined as the presence of an HbA1c value $< 7.0\%$ any time 60 to 180 days after the index date.

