9.7.3 Secondary Analysis

For the secondary analysis, results will be stratified by age, renal function, and race/ethnicity. Comparisons of pre-index characteristics and outcome measures across age, renal function, and race/ethnicity strata will be provided, and appropriate tests will be used based on the distribution of the measure. Continuous measures will be compared using t-tests and categorical measures will be compared using chi-square tests. P-values and 95% confidence intervals will be reported. Reported p-values will not be adjusted for multiple comparisons.

In addition, as part of the secondary analysis, multivariable modelling will be considered to assess change in HbA1c, controlling for an a priori list of covariates. The use of multivariable modelling will be dependent on having robust sample size distribution (as defined in Section 9.5 Study Size) across age and eGFR categories.

Since the primary outcome of change in HbA1c is calculated using just two timepoints, pre-index and follow-up, multivariable analysis will be conducted using ordinary least squares (OLS). In the event that the assumption that the majority of patients have only one HbA1c measure during the follow-up period turns out to be false and there are multiple HbA1c values per patient during this timeframe, mixed models repeated measures (MMRM) will be used to control for the correlation of multiple HbA1c observations from the same patient.

Following standard procedure, regression diagnostics will be performed for each model to assess goodness of fit and violations of model assumptions (e.g., multicollinearity,

heteroskedasticity). When there are violations of the model, Optum will note them and make appropriate corrections to the data (i.e., typically through transformation of either the independent or dependent variables) or in the method of estimation.

The following list of covariates will be included in the model provided sufficient sample size distribution:

- Age categories (40 to 54 years, 55 to 64 years, 65 to 74 years, and ≥ 75 years)
- Sex
- Race
- Ethnicity
- Geographic region
- Pre-index HbA1c
- Pre-index renal function categories based on eGFR (< 30 ml/min/1.73m², 30 to 44 ml/min/1.73m², 45 to 59 ml/min/1.73m², 60 to 89 ml/min/1.73m², and ≥ 90 ml/min/1.73m²)
- Pre-index Quan-Charlson comorbidity score

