9.9 LIMITATIONS OF THE RESEARCH METHODS

This study has several limitations inherent to its non-interventional study design. There may be baseline differences in the different age and renal function categories. In randomized clinical trials, these differences are mitigated by randomization. Among the important considerations is if there are substantial differences in baseline HbA1c. It is well known that the change from HbA1c is a function of baseline HbA1c, ie, the higher the baseline HbA1c, the greater the change from baseline even with comparable doses of the glucose lowering medication. This observation has been confirmed by Esposito et al (22) in their analyses of several DPP4 inhibitors.

Second, we have selected a follow up window of 6 months rather than a longer window e.g. up to 1 year. Maximal effectiveness is usually achieved by 6 months, although in randomized controlled trials HbA1c values may be lower at later time points. This limitation is balanced against the observation that medication persistence at 6 months will likely be

better than at 12 months and the fact that we wish to maximize the numbers of patients in each of the age and renal function cells.

Third, duration of T2DM is likely to be longer in patients with lower renal function. Increased duration of diabetes is also associated with greater reductions in beta cell function. Since one of the mechanisms of DPP4 inhibitor medications is to increase GLP-1 mediated insulin secretion, reduced renal function could theoretically be associated with diminished glycemic effectiveness. If the current study supports this observation, this will confound the claim of comparable glycemic effectiveness across the range of renal function, but it will be an important observation for the management of T2DM patients. Lajra et al reported on a retrospective analysis of 202 patients from two separate trials in which patients with > 10 years of diabetes were randomized to linagliptin 5 mg (n = 122) or placebo (n = 80)(15). The placebo adjusted mean difference in HbA1c was -0.66% (95% CI -0.85 to -0.38). No direct comparisons were made with shorter duration of diabetes. However, these data suggest that differences in duration of diabetes are unlikely to have a major effect on the data obtained in the current proposal.

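### HbA1c goal attainment is compared across age and eGFR strata only by an unadjusted chi-square test, although it depends on pre-index HbA1c and patients already below 7.0% count as successes

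*Combined protocol and SAP*

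**What the plan says.** Section 8 gives two secondary objectives. The second begins "Compare the proportion of adults with T2DM who achieve HbA1c" and sets the threshold at 7.0%, across the age and renal function categories. Section 9.3.2.2 defines the outcome: "HbA1c goal attainment will be defined as the presence of an HbA1c value" below 7.0% at any time from day 60 to day 180. The definition places no condition on the pre-index value.

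Section 9.2.2 requires "≥ 1 HbA1c value during the 180-day pre-index period or on the index date" but sets no lower limit, and none of the exclusions in Section 9.2.3 removes patients who are already below 7.0%.

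For analysis, the Abstract states: "Continuous measures will be compared using t-tests and categorical measures will be compared using chi-square tests". Section 9.7.3 repeats this ("categorical measures will be compared using chi-square tests") and adds that "multivariable modelling will be considered to assess change in HbA1c, controlling for an a priori list of covariates". The methods named there are OLS, or MMRM if patients have several follow-up values. Pre-index HbA1c is on the covariate list, but the only model described is for change. No adjusted model for the binary outcome appears.

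Section 9.9 accepts that strata may differ at baseline: "Among the important considerations is if there are substantial differences in baseline HbA1c". It also says that "the higher the baseline HbA1c, the greater the change from baseline".

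**The concern.** Follow-up HbA1c is pre-index HbA1c plus change. Whether it falls below a fixed 7.0% therefore depends on where the patient started as well as on the drug. Two strata with the same effect at every baseline, but different mean baselines, will differ in attainment. Equally, a stratum with a weaker effect but a lower baseline can look the same as the others. The plan lists pre-index HbA1c for adjustment in the change model but leaves the attainment comparison uncorrected.

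Section 9.1 names attainment, beside change in HbA1c, as a measure of whether effectiveness is comparable across age and renal function. A chi-square p-value driven by baseline imbalance could be read as an answer to that question in either direction.

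**Working it through.** **The plan's own figures.** The documents give no power or expected rate for attainment. The only sample sizes (Section 9.5) are for a 0.5 difference in mean change, with 80% power and two-sided alpha 0.05. The normal formula n = 2(1.960 + 0.842)² × SD² / 0.5² gives 90.4 (91) for SD 1.2 and 141.3 (142) for SD 1.5. The exact t calculation gives the stated 92 and 143.

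**Inputs for the illustration**
- From the plan: SD of change 1.2 to 1.5 and 143 per group (Section 9.5); age cells of more than 2,500 and more than 3,000 (Section 9.7.1), taken as 2,500 and 3,000.
- Assumed: normal values, baseline SD 1.3, mean change -0.6 at a baseline of 8.0, and an extra reduction s of 0 to 0.5 per point of baseline. Section 9.9 supports the direction of s but gives no size.
- One follow-up value per patient, as Section 9.3.2.1 expects for most patients.

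**Formula.** For mean baseline m:
- follow-up mean = m - 0.6 - s(m - 8)
- follow-up variance = (1 - s)² × 1.3² + SD² - (1.3s)²
- attainment = Φ((7 - mean)/√variance)

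**Worked case**, s = 0.3, SD 1.2, mean baselines 7.9 and 8.1:
- Variance = 0.8281 + 1.44 - 0.1521 = 2.116, so the SD is 1.455.
- Follow-up means are 7.33 and 7.47, and attainment is 41.0% and 37.3%, a gap of 3.7 points.
- With 2,500 v 3,000 patients the pooled proportion is 0.390 and the standard error 0.0132. The expected z is 0.037/0.0132 = 2.80, and the rejection rate is about Φ(2.80 - 1.96) = 80%.

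**Attainment with the same effect at each baseline, full range of s and SD**

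| Mean baseline | Attainment | Already below 7.0% before linagliptin |
|---|---|---|
| 7.5 | 45-52% | 35% |
| 8.0 | 37-42% | 22% |
| 8.5 | 29-33% | 12% |

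**Spurious gap and chi-square rejection, groups centred on 8.0**

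| Baseline difference | Gap (points) | p<0.05, 2,500 v 3,000 | p<0.05, 143 v 143 |
|---|---|---|---|
| 0.1 | 1.3-2.2 | 16-38% | about 5-6% |
| 0.2 | 2.6-4.4 | 49-91% | about 7-11% |
| 0.3 | 3.8-6.6 | 83-99.9% | about 10-20% |

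**Masking.** Attainment is equal when (1 - s) × baseline difference = effect difference. A stratum with a 0.2-point weaker effect looks the same if its mean baseline is lower by 0.2/(1 - 0) = 0.2, or by 0.2/(1 - 0.5) = 0.4.

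**Does adjustment work?** Data were simulated with no true stratum effect, 2,500 v 3,000 patients, and baseline differences of 0.2 and 0.3. Crude chi-square rejected in 50-99.8% of runs. Restricting to pre-index HbA1c of 7.0% or more still rejected in 16-66%, with gaps of 1.4-3.3 points. Logistic regression with continuous pre-index HbA1c rejected in 4.6-5.6%, with a mean odds ratio of 1.00. At 143 v 143 and a difference of 0.3, it rejected in 4.5-5.2%.

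**The case against.** **An adjusted analysis may exist elsewhere.** Section 9.2.3 points to a Section 9.7.4.4, and Section 12 to a separate analysis plan; neither is in the supplied text. Section 9.3.3.2 also defines pre-index HbA1c categories at 8% and 9% that no supplied analysis uses. However, 9.7.4.4 is cited only for drugs added during follow-up and is not in the table of contents. The analysis plan is cited only for table shells, and the 8% and 9% categories are not tied to attainment. The limit to the supplied text stands.

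**The upper figures use s = 0.** Section 9.9 says change does depend on baseline, and that dependence narrows the attainment gap. This is fair. With s of 0.3 to 0.5, the gaps are 1.3-1.9, 2.6-3.7 and 3.8-5.5 points, and rejection at 2,500 v 3,000 is 16-29%, 49-80% and 83-99%. The bias is smaller but remains.

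**The age cells are feasibility counts.** They do not reflect every final criterion, so the analysed cells may differ. No eGFR cell sizes are given.

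**Adjustment is not perfect.** If a single baseline value carries an assumed within-person SD of 0.5 and true means differ by 0.3, adjusted logistic regression rejected in about 14-15% of runs (2,500 v 3,000). That is above nominal but far below the crude test. An odds ratio also does not directly give the proportion named in the objective.

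**The study is exploratory.** The primary analysis is descriptive, baseline imbalance is a stated limitation, pre-index HbA1c is reported by stratum, and an adjusted model is considered for change. This limits the consequence, but none of it corrects the attainment comparison, for which p-values and confidence intervals will be reported.

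**Conclusion.** The concern holds for the supplied text. Attainment is a secondary comparison with no planned adjustment for pre-index HbA1c, and patients already at goal count as achieving it. That attainment depends on baseline follows from the definition of the outcome and needs none of the assumed figures. The size does: it rests on the assumed baseline distribution, mean change and slope, and nothing in the documents shows how large any imbalance will be.

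In the large age cells a difference of only 0.2 in mean baseline could make a spurious p<0.05 about as likely as not, or much more likely. In cells near 143 the rates are distorted equally but significance is uncommon. The primary descriptive analysis of change is not affected. The plan should be changed, because the correction is cheap and uses a covariate already collected.

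**What to change.** In Section 9.7.3, add a logistic regression for goal attainment with continuous pre-index HbA1c and the other covariates listed for the change model, under the same rules for collapsing age and eGFR categories. Make this the basis for comparing strata, and keep the crude proportions as description. Model-based proportions standardised to a common baseline distribution could accompany the odds ratios, since the objective is about a proportion.

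As a supplement, tabulate attainment separately for pre-index HbA1c below 7.0% and 7.0% or above, removing no one from the overall population. This split does not replace the model, because restriction alone leaves much of the bias. A sensitivity analysis defining attainment on the last value in the 60 to 180 day window is optional.

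If the separate analysis plan already contains such a model, Section 9.7.3 needs only to say so.

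The cost is one paragraph and one supplementary table. All variables are already collected. The downsides are a little more analysis work and smaller denominators in the split table.

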7. RATIONALE AND BACKGROUND

Patients with type 2 diabetes mellitus (T2DM) have progressive decline in renal function and this decline in function is greater than age-related decline in patients without diabetes (1-4). Selection of glucose lowering agents is often affected by the level of renal function. Dipeptidyl peptidase-4 (DPP-4) inhibitors are approved to treat hyperglycemia among adults with T2DM with a wide range of renal function. In contrast to most other DPP-4 inhibitors (5), linagliptin does not require dose adjustment as renal function declines. Without further requirement of dose adjustment, linagliptin affords simplicity for chronic management of HbA1c.

Current literature indicate that decline in renal function is also associated with glycemic control, hypertension, albuminuria and dyslipidemia (9-11). However, there is limited evidence about the real world effectiveness and safety of linagliptin across different age and renal functions among adults with T2DM.

Data from clinical studies demonstrate that the expected reduction in HbA1c should be similar across the range of ages, but direct comparisons with younger patients are not available. Barnett et al reported on 238 patients aged 70 or older randomized to linagliptin 5 mg daily (n = 160) or placebo (n=78). The placebo adjusted mean difference in HbA1c after 24 weeks was -0.64% (95% CI -0.81 to -0.48) (12). Inzucchi et al reported on 247 patients aged 70 or older randomized to linagliptin (n = 126) or placebo (n = 121) added to basal insulin (13). The placebo adjusted mean difference in HbA1c after 24 weeks was -0.77 (94% CI -0.95 to -0.59). These values are consistent with other studies of linagliptin, but do not provide direct comparison data with younger patients.

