9. RESEARCH METHODS

9.1 STUDY DESIGN

This will be a non-interventional cohort study using existing data from patients in the Optum Clinical Database which contains electronic health record (EHR) data from providers across the United States.

Real-world EHR data will be used to determine whether there is comparable effectiveness of linagliptin 5 mg daily on glycemic effectiveness as determined by the change in HbA1c and the percentage of patients achieving an HbA1c goal of < 7.0% during the 60 to 180 days after initiation of linagliptin across a range of age and renal function categories.

[figure not shown]

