9.3.3.2 Clinical Characteristics

- Pre-index Quan-Charlson comorbidity score—Quan-Charlson comorbidity score will be calculated based on the presence of diagnosis codes in the pre-index period (including the index date) (16). The Quan-Charlson comorbidity score will also be categorized into the following groups: zero, one to two, three to four, and five or more.
- Pre-index comorbid conditions-General comorbid conditions will be defined using the Clinical Classifications Software managed by the Agency for Healthcare Research and Quality (AHRQ) (17). This measure generates indicator variables for specific disease conditions based on diagnosis codes. The top 20 comorbid conditions will be presented.
- Pre-index antihyperglycemic medications— Pre-index antihyperglycemic medications will be identified based on written prescription, medication administration, and medication history records in the EHR data during the pre-index period. Binary flags, one per medication class and another per distinct medication based on generic name, will be created for the antihyperglycemic medications. Medication classes will be determined using the “Medication Class” column in Tables 2 through 13 of [Annex 1, Appendix B](#) and will include metformin, sulfonylureas, meglitinides, thiazolidinediones (TZDs), DPP-4 inhibitors other than linagliptin, glucagon-like peptide-1 receptor agonists (GLP-1RA), sodium-glucose co-transporter 2 (SGLT2) inhibitors, basal insulins, bolus insulins, mixed insulins, alpha glucosidase inhibitors, and amylin analogs. Combination products containing two medication classes will be considered as two distinct medication classes. Distinct medications will be determined using the “Medication Name” column in Tables 2 through 13 of [Annex 1, Appendix B](#). Combination products containing two generic ingredients will be considered as two distinct antihyperglycemic medications.

- Pre-index antihyperglycemic therapy categories—Patients will be categorized into one of the following groups based on the medication class for their pre-index antihyperglycemic therapies:
 - Metformin only
 - Sulfonylurea only
 - Meglitinide only
 - TZD only
 - GLP-1RA only
 - SGLT2 inhibitor only
 - Basal insulin only
 - Metformin + sulfonylurea
 - Other combination (additional groups will be created for any medication class combinations that are present among least 5% of the study sample)

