9.5 STUDY SIZE

This study is exploratory and not characterized with *a priori* hypotheses. All patients identified in the data that meet the inclusion criteria and do not meet the exclusion criteria will be included in the study population.

A sample size calculation was conducted to determine the minimum number of patients that would be required to detect a change in HbA1c of at least 0.5% among the cohort groups. Based on previously published studies, it was assumed that the standard deviation for the 24-

week mean change in HbA1c from baseline could range between 1.2 (based on the placebo adjusted value in the MARLINA-T2D trial (20)) and 1.5 (based on retrospective studies of diabetes treatments using electronic medical record data from across the United States (21)). Assuming a SD of 1.2 for the change in HbA1c, at least 92 patients would be needed in each of the two smallest groups of the cohort of interest (e.g., age, renal function, age by renal function) in order to have 80% power to detect a mean difference in HbA1c of at least 0.5% using a two-sided test at an alpha of 0.05. If the standard deviation for the change in HbA1c is 1.5, then 143 patients would be needed in each of the two smallest groups.

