9.7 DATA ANALYSIS

9.7.1 Feasibility Assessment

Feasibility analyses will include determinations of the number of patients in each potential category of age and renal function. Some cells may be too small (e.g. eGFR 30 to 44 ml/min/1.73m²), but as long as most of the key groups have sufficient numbers (as described in Section 9.5 Study Size) of patients this will not detract from the overall results. The number of AA individuals will not be as large as the full data set and as such some of the age and eGFR groups will be much smaller than for the whole group. Since the AA subgroup analysis is exploratory, having some small groups will not significantly limit the overall clinical interpretation even if statistical comparability cannot be confirmed.

Optum conducted a feasibility analysis using data from the Optum EHR database. There were 63,499 patients identified with a written prescription for linagliptin between January 1, 2012 and June 30, 2016. After excluding patients without data available for a six-month pre-index period, patients with a prescription for linagliptin or other DPP-4 inhibitor, and patients less than 40 years of age, the patient count was reduced to 38,868 patients.

A total of 16,566 patients had at least one HbA1c result during the six-month period prior to the index date and at least one HbA1c result during the six-month period after the index date. Of these, 16,566 adult patients were newly initiated on linagliptin with baseline and follow-up HbA1c results, race/ethnicity was available in 15,289 patients, a serum creatinine value was available for 15,130 patients, and both race/ethnicity and serum creatinine were available for 13,962 patients.

Among the 13,962 patients meeting the criteria and with a baseline serum creatinine, the smallest age group cell (40-54 years) had more than 2,500 patients and the cell with age > 75 years (which is of special interest in this protocol) had more than 3,000 patients. Thus, for the primary end point to assess HbA1c across age ranges, each category is of sufficient size to conduct this study.

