- Pre-index individual comorbidities (each of the AHRQ top 20 comorbidities identified for this population will be included unless the comorbidity is already included in the Charlson Comorbidity Index)

Age and renal function categories will be assessed for adequate sample size across categories based on the sample size calculation reported in Section 9.5. If the sample size distribution is not sufficient to evaluate age as a categorical variable, age will be included as a continuous variable in the model. The eGFR categories of 45 to 59 ml/min/1.73m² (Stage 3A kidney disease) and 30 to 44 ml/min/1.73m² (Stage 3B kidney disease) will be collapsed into one category (Stage 3 kidney disease) if there is not sufficient sample to evaluate as separate categories.. If the sample size distribution is still not sufficient across the eGFR categories, then eGFR will be included as a continuous variable in the model.

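### The adjusted model for the age and renal comparisons has no pre-index antihyperglycemic therapy term, although the class flags are already built; report the contrasts with and without them

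*Combined protocol and SAP*

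**What the plan says.** Section 9.7.3 first compares outcomes across strata with t-tests and chi-square tests. It then says that "multivariable modelling will be considered to assess change in HbA1c, controlling for an a priori list of covariates", subject to adequate numbers in the age and eGFR categories. Estimation is by OLS, or by MMRM if most patients turn out to have several follow-up values; no separate covariate list is given for MMRM. No adjusted model is described for reaching HbA1c below 7.0%.

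The list begins "The following list of covariates will be included in the model provided sufficient sample size distribution". It names age category, sex, race, ethnicity, region, pre-index HbA1c, eGFR category, Quan-Charlson score and individual comorbidities, where "each of the AHRQ top 20 comorbidities identified for this population will be included" unless already in the Charlson index. The covariate list in the abstract has no therapy item either.

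The therapy data are planned. Section 9.3.3.2 states: "Binary flags, one per medication class and another per distinct medication based on generic name, will be created for the antihyperglycemic medications". It names 12 classes. Section 7 gives the link to the renal comparison: "Selection of glucose lowering agents is often affected by the level of renal function".

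On purpose, Section 9.1 sets this aim: "determine whether there is comparable effectiveness of linagliptin 5 mg daily on glycemic effectiveness as determined by the change in HbA1c". Goal attainment is the second measure, and both are looked at by age and renal category. Section 9.5 adds: "This study is exploratory and not characterized with" a priori hypotheses.

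**The concern.** If background therapy differs between eGFR categories, and also predicts HbA1c change at equal pre-index HbA1c and comorbidity, the adjusted eGFR contrast contains both renal function and background therapy. A reader could not tell the parts apart. The mixture could produce a difference or hide one, and hiding one would favour a conclusion of comparable effectiveness. With no comparator arm (Section 9.9), that conclusion rests on contrasts between strata.

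Section 9.9 acknowledges in general that age and renal categories may differ at baseline, and it discusses baseline HbA1c and diabetes duration. Neither Section 9.9 nor Section 9.12 names background therapy as a limitation.

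The same mechanism is possible for age, but that is an inference; the protocol states the link only for renal function.

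**Working it through.** **1. The plan's own figures.** Inputs from Section 9.5: difference 0.5, SD 1.2 or 1.5, two-sided alpha 0.05, power 80%. The two-sample t-test solution is 91.39 and 142.25 per group, which rounds up to the stated 92 and 143. They reproduce.

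**2. How omission acts.** In OLS, for a given eGFR category against the reference:

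coefficient without flags − coefficient with flags = sum over classes of (adjusted prevalence gap × adjusted class effect).

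This is an algebraic identity, not evidence that a shift exists here. Classes may add or offset.

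**3. What would be needed.** The documents give no therapy distribution by stratum and no class effects, so the gaps below are assumed. For one class, effect needed = shift ÷ gap:

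| Shift (HbA1c points) | Prevalence gap | Class effect needed |
|---|---|---|
| 0.10 | 0.25 | 0.10/0.25 = 0.4 |
| 0.10 | 0.50 | 0.10/0.50 = 0.2 |
| 0.50 | 0.50 | 0.50/0.50 = 1.0 |

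A shift of 0.10 is one fifth of the 0.5 planning difference. Over assumed gaps of 0.1 to 0.4 and effects of 0.2 to 0.5, the single-class shift runs from 0.1 × 0.2 = 0.02 to 0.4 × 0.5 = 0.20.

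**4. Sampling error for comparison (unadjusted SEs).** Half-width of the 95% CI = 1.96 × SD × √(1/n₁ + 1/n₂).

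- Section 9.5 minimum cells: 1.96 × 1.2 × √(2/92) = 0.347; 1.96 × 1.5 × √(2/143) = 0.348. A 0.10 shift would be lost in this.
- Age cells from Section 9.7.1, where "the smallest age group cell (40-54 years) had more than 2,500 patients" and the oldest had more than 3,000: at most 1.96 × 1.2 × √(1/2500 + 1/3000) = 0.064, or 0.080 with SD 1.5. If later criteria halve these cells (assumed), 0.090 and 0.113. A 0.10 shift could matter here.

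The documents give no eGFR cell counts. For the contrast with the documented mechanism, sensitivity to a 0.10 shift is therefore unknown.

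**5. Size of the enlarged model.** Terms in the listed model: age 3, sex 1, race 3, ethnicity 3, region 4, HbA1c 1, eGFR 4, Charlson 1, comorbidities up to 20 = 40. Section 9.2.3 excludes prior DPP-4 inhibitor users, so that flag is constant and 12 − 1 = 11 flags can vary. That makes 51 terms, or 52 with an index-date flag. At the feasibility count, 13,962/52 ≈ 268 patients per term; at half that, 6,981/52 ≈ 134.

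**6. Precision.** SE factor = 1/√(1 − R²), where R² is the share of the remaining variance of an eGFR indicator explained by therapy. With assumed R² of 0.05 and 0.30 the factors are 1.03 and 1.20, before any gain from lower residual variance.

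**The case against.** The strongest reply is that leaving therapy out is a legitimate choice of question. The title and aim are real-world effectiveness, the study is exploratory, and if renal function drives drug choice then therapy is partly a consequence of eGFR. Adjusting for it answers a different question. This stands. A reader might infer that the planned model is wrong, or its eGFR contrast biased; the documents do not support that. They support only that one of two useful contrasts is described, and that it alone cannot answer the comparability question at equal background therapy.

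The plan also has real mitigations. Prior DPP-4 inhibitor users are excluded, as by default are patients starting another new agent on the index date. Pre-index HbA1c and comorbidity are in the model and may absorb part of any shift. Pre-index characteristics are compared across strata, so imbalance would be seen. But seeing an imbalance does not give a contrast at equal therapy.

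Three further inferences go too far:

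- *That no other adjusted analysis is planned anywhere.* Section 12 and Appendix C point to an analysis plan that is not supplied, and the reference to Section 9.7.4.4 suggests further analysis text. The statement holds for the supplied text only.
- *That the large age cells show the renal contrast to be sensitive.* The stated mechanism is for eGFR, the known counts are for age, and no contrast has both.
- *That co-initiators are ignored if the Section 9.2.4 waiver is used.* They are flagged for a subanalysis; the flag is simply not in the model list.

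**Conclusion.** The point holds for the supplied text: the adjusted model has no pre-index therapy term, although the flags exist and the protocol itself links drug selection to renal function. The planned eGFR contrast is one among patients as treated, and it cannot separate renal function from background therapy. This bears on the secondary comparisons and on how Section 9.1 can be answered. It does not touch the primary descriptive analysis.

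The documents do not allow the size or direction of the shift to be estimated, and it may be zero; every gap and class effect used above is assumed. The case for change rests on interpretability at low cost, not on a demonstrated bias.

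One related matter is a query only. Section 9.2.3 sends therapy added during follow-up to a sensitivity analysis in Section 9.7.4.4, which is in neither the contents list nor the supplied text. A reader might infer that the analysis was never planned; it may sit in the analysis plan or in text not supplied.

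**What to change.** 1. Keep the Section 9.7.3 model and prespecify a second that adds the 11 pre-index class flags that can vary. Report age and eGFR contrasts from both models in the same patients, labelled *as patients are treated* (without flags) and *at equal background therapy* (with flags). State that the flags record any use in the 180 days before index, not necessarily use continuing at index.
2. If the Section 9.2.4 waiver is used, also put the index-date new-drug flag in the model, in addition to the subanalysis already planned.
3. Confirm where the Section 9.7.4.4 sensitivity analysis sits and correct the reference in Section 9.2.3.

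The cost is protocol wording, one more model to report and minor programming on variables already defined. The flags record presence or absence, so they should remove no patients. The loss of precision falls only on the added contrasts; the planned contrasts keep theirs.
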